#### 7.3 Randomisation

Randomisation shall occur pre-operatively once the patient has been deemed eligible for the study, provided written informed consent and their baseline procedures completed. The randomisation sequence is pre-determined by LCTC, see section 11.1 for further details.

**IRAS Ref: 271885** Page 39 of 89

The randomisation will be processed using REDCap, a commercially available on-line research database system, and will be processed by the research team at the recruiting site. It should be completed as soon as possible for the purposes of operation list planning and implant procurement, and must be no later than the day prior to surgery. The only caveat to this deadline is for patients who will not be consented until the day of their surgery, in which case randomisation should be completed as soon as it is possible to do so.

## 7.4 Day of Surgery and In-Patient stay

Clinical data, including length of stay in hospital, changes to the type of implant used and safety data will be collected during this period. Specific information on reporting adverse events can be found in section 12.

Following the surgery, the scrub team will complete an intraoperative healthcare resource use questionnaire collating source data on length of surgery and usage of equipment and disposables during surgery etc.

## 7.5 6 weeks post-op

All patient participants will be reviewed in a routine outpatient clinic at 6 weeks postoperatively (from date of surgery). Please also see section 7.12 on contingency planning.

PROMS questionnaires to be completed are listed below. The Oxford Hip Score is to be completed first, others are shown in a recommended order of completion of most recent recall period:

- Oxford Hip Score
- EQ-5D-5L™
- Self-Administered Patient Satisfaction scale
- Forgotten Joint Score
- Work Productivity and Activity Impairment—Specific Health Problem

Data will also be collected Adverse Events of Special Interest; these will primarily be surgical complications, such as but not limited to returns to theatre for dislocation, fracture or wound problems; any prescriptions for antibiotics will be noted and any unanticipated contact with the surgical team or GP regarding the surgery.

The earliest this visit can occur is 3 weeks postop and the latest is 12 weeks postop from the date of surgery. Visits outside of these parameters will be recorded as protocol deviations but will not affect the patients continuing participation in the trial.

Every effort should be made to meet the patient in person during the visit. Should this not be possible the questionnaires should be posted as soon as possible to the patient for their completion. Details on how and when to return the questionnaires are included within the covering letter. (See also section 7.7 Loss to follow-up.)

## 7.6 3-6 month post-op

Patient participants will be required to complete their PROMS questionnaires and healthcare resource use survey between 3 and 6 months postoperatively (from date of

**IRAS Ref: 271885** Page 40 of 89

surgery). This follow-up period will be dictated by the remaining duration of the study. All patient participation activity is expected to be completed by the end of October 20201. See the table below.

Month of Operation	Follow-up time point	Follow-up duration
January '21	July '21	6 months
February '21	August '21	6 months
March '21	September '21	6 months
April '21	October '21	6 months
May '21	October '21	5 months
June '21	October '21	4 months
July '21	October '21	3 months

PROMS questionnaires and a healthcare resource use survey will be sent in the post for the patient participant to complete. The accompanying cover letter will advise that the Oxford Hip Score is to be completed first, others are shown in a recommended order of completion of most recent recall period:

- Oxford Hip Score
- EQ-5D-5LTM
- Self-Administered Patient Satisfaction scale
- Forgotten Joint Score
- Work Productivity and Activity Impairment-Specific Health Problem
- Healthcare Resource Use Survey

A member of the hospital research team will contact the patient participants by phone before distribution to inform them of the upcoming postal questionnaires. The questionnaires should be posted early enough that the patient participant is in possession of them at the required 3-6 month post-operative date.

Patient participants will also be asked about any return to theatre required and any unanticipated contact with the surgical team or GP regarding the surgery.

The earliest that this data can be collected is 4 months postoperatively and the latest time is 8 months. Completion of these questionnaires outside of these parameters will be recorded as protocol deviations but will not affect the patients continuing participation in the trial.

Details on how and when to return the questionnaires are included within the covering letter.

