#### Secondary

#### To Assess:

- 1. Recruitment to a trial of this nature
- 2. Capture rate for postal/telephone follow-up
- 3. Rate of trial withdrawal
- 4. PROMS data statistics to determine the power required for the full study
- 5. Intra-operative and post-operative safety
- 6. To identify the incidence of treatment cross over during surgery
- 7. To determine the feasibility of conducting a within-trial cost-utility analysis

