## 5.2.3 Withdrawal from Trial Completely

The patient participant can withdraw consent at any time without providing a reason.

Patient participants who wish to withdraw consent for the trial will have pseudonymised data collected up to the point of withdrawal of consent included in the analyses.

Participants who withdraw from the trial completely will not contribute further data to the trial, unless this is required under applicable legislation (e.g. safety events) - the LCTC should be informed in writing and a withdrawal CRF should be completed.

Patient participants who have provided consent and been randomised, and whose surgeries are delayed beyond the agreed time-point for participation in the study will be withdrawn. This date will be advised to sites in advance. These participants will return to their normal clinical care pathway. They will not be replaced and follow-up data will not be collected.

**IRAS Ref: 271885** Page 34 of 89

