## 7.7 Loss to follow-up

If after posting the questionnaires to the patient their return is not forthcoming, two reminder telephone calls should be made to them. If these calls prove unsuccessful, a reminder letter should be sent.

The timing of the reminder calls and letter is at the discretion of the treating hospital, however a suitable time-frame should be implemented and care should be taken in the timing of the final reminder letter so it allows sufficient time for the completion of the questionnaires within the stipulated +/- allowance for the post-op time point.

**IRAS Ref: 271885** Page 41 of 89

If no reply is received after the letter has been posted and sufficient time allowed for completion and return of the questionnaires, the patient shall be classed as lost to follow-up and the relevant CRF completed and provided to LCTC.

**IRAS Ref: 271885** Page 42 of 89

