## 7.8 Schedule of trial procedures

Table B below describes Workstream 1 procedures and their time-points.

Table B: Trial procedures

able B. That procedures						
	TIMEPOINT					
PROCEDURE	Screening	Baseline	Randomisation	Day of surgery	Routine 6 weeks Post-op (-3 weeks / +6 weeks)	3-6 months Post-op (-2 month / +2 months^)
Identify eligible patient from records	Х				•	
Approach patient and discuss trial	Х					
Obtain Consent	Х					
Randomise patient			Х			
Demographics	Х					
PROMS – Oxford Hip Score		Х			Х	Х
PROMS – EQ-5D-5L TM		Х			Χ	X
PROMS – Self-Administered Patient Satisfaction Scale					X	X
PROMS – Forgotten Joint Score		Х			Х	Х
PROMS – Work Productivity and Activity Impairment–Specific Health Problem		Х			Х	Х
Healthcare Resource Use Survey		Х				Х
Data collection on routine surgery				Х		
Report Serious Adverse Events or Incidents				X	X	Х

^Yet no later than October 2021

**IRAS Ref: 271885** Page 43 of 89

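### Final questionnaires for April–July operations fall due in the month collection is capped, so some patients may not get the full reminder sequence and postal capture may be understated

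*Protocol*

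**What the plan says.** The table in section 7.6 gives each month of operation a follow-up month and a duration. January, February and March operations fall due in July, August and September, all at 6 months. The next rows read "April '21 October '21 6 months", "May '21 October '21 5 months" and "June '21 October '21 4 months", and July operations are also due in October, at 3 months. The same section states that "All patient participation activity is expected to be completed by the end of October 20201"; the year is misprinted and the table shows that 2021 is meant. Table B in section 7.8 gives the time-point an allowance of two months either side, with the footnote "Yet no later than October 2021".

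Section 7.7 deals with forms that do not come back: "two reminder telephone calls should be made to them. If these calls prove unsuccessful, a reminder letter should be sent". Hospitals choose the timing, but the letter must leave time for completion within the stipulated allowance. A patient is classed as lost only after the letter and enough time for a reply.

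A secondary objective in section 2.3 is "Capture rate for postal/telephone follow-up". Section 2.2 says the loss to follow-up rate for the proposed collection method is needed to size the full trial.

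**The concern.** Section 7.7 depends on an allowance that section 7.6 and Table B largely remove for the later operations. A patient operated on at the end of July reaches 3 months on the last day of October, so no sequence of two calls and a letter fits between that date and the cap. January and February patients can be chased for the whole two months.

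Lost chase time can only lower measured capture relative to a full chase. The affected patients are the later ones, and from May onwards also those with the shorter follow-up, so the effect of a cut-short chase cannot be separated from that of follow-up length. Section 7.7 has no category for a chase stopped by the calendar. If such non-returns were counted as losses, the loss rate carried into the full trial's sample size would be too high. Retention is also part of the feasibility judgement in section 11.5.

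**Working it through.** **The plan's own figures.** Duration equals follow-up month minus operation month: 7−1, 8−2, 9−3, 10−4, 10−5, 10−6, 10−7 = 6, 6, 6, 6, 5, 4, 3 months. All seven rows of the section 7.6 table reproduce.

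**Time left after the nominal date.** The table gives a month and no day, so I take the nominal date as operation date plus tabulated duration. Slack is 31 October 2021 minus that date.

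| Operation month | Slack (days) | Two-month allowance intact? |
|---|---|---|
| January | 92–122 | yes |
| February | 64–91 | yes |
| March | 31–60 | partly cut |
| April | 1–30 | cut |
| May | 0–30 | cut |
| June | 1–30 | cut |
| July | 0–30 | cut |

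The full plus side would be 61–62 days.

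**Share of patients without time for the chase.** The protocol states neither the number of operations per month nor the length of the chase. I assume operations spread evenly over the 212 days from 1 January to 31 July, and a chase of 14, 21 or 28 days. The share is the number of operation dates with slack below the chase length, divided by 212.

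- *Clock starts at the tabulated date.* 14 days: (13+14+13+14)/212 = 54/212 = 26%. 21 days: (20+21+20+21)/212 = 82/212 = 39%. 28 days: (27+28+27+28)/212 = 110/212 = 52%.
- *Posting at 4 months, the earliest collection named in section 7.6.* April and May always have enough time (62–91 and 31–60 days). June contributes 13, 20 or 27 dates. All 31 July dates count, because July operations reach 4 months only in November. Results: 44/212 = 21%, 51/212 = 24%, 58/212 = 27%.
- *Posting at 3 months, the lower end of the stated range.* Only July is short: 14/212 = 7%, 21/212 = 10%, 28/212 = 13%.

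Out of 40 patients these ranges are about 10–21, 8–11 and 3–5.

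**Effect on capture.** The shortfall is the share cut short times the percentage points of return lost in that group. For every 10 points lost there, overall capture falls by 0.7 points (0.066 × 10) to 5.2 points (0.519 × 10). The protocol gives no figure for what reminders recover, so the actual size cannot be stated.

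**The case against.** A reader might infer that the chase is cut short for most of the sample. The protocol does not support that. Being due in October is not the same as being cut short: the chase runs from posting, forms are posted ahead of the due date, and hospitals set the reminder timing. The 3–6 month range, and even the 4-month minimum, lets April and May patients be posted well before October. A majority appears only with a chase of about 28 days counted from the tabulated dates.

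Nor does the protocol support saying that these patients would be recorded as lost. Read literally, section 7.7 classes a patient as lost only after a completed chase. What is missing is a rule for an incomplete one.

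The stop is also softer in section 7.6, which says expected, than in Table B. Late forms are recorded as deviations and do not end participation, and section 8.1.2 defines trial end as the data freeze. Under section 5.2.3, patients "whose surgeries are delayed beyond the agreed time-point for participation in the study will be withdrawn"; that date is not printed, so the late-July group may be small.

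Finally, any bias may be smaller than sampling error: at an assumed 85% capture, 1.96 × √(0.85 × 0.15/40) = 0.11, or 11 points either way. The numerical stop/go thresholds are recruitment counts, and retention enters only through serious issues.

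All of this limits the size of the point. It does not help July operations, whose 3-month date already falls in October. Table B's two-month minus side might be read as allowing earlier collection, but that conflicts with the 4-month minimum. Sampling error does not excuse a shift in a known direction that can be avoided.

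**Conclusion.** The concern holds in limited form. It is certain that April–July operations are all due in October 2021, that collection is capped in that month, and that the time after the nominal date falls to 0–30 days. July operations may not get a complete chase, nor may June operations if posting waits for 4 months. April and May operations are at risk only if sites wait for the tabulated month.

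Capture may be biased low relative to the method the full trial would use, and loss to follow-up correspondingly high if an incomplete chase is counted as loss. The shares of 7–13%, 21–27% and 26–52% rest on even accrual and a 14–28 day chase, neither of which is stated. The bias in percentage points cannot be derived from the protocol. This is a modest, correctable weakness in quantities the study sets out to estimate.

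**What to change.** 1. In section 7.6 and the Table B footnote, make October 2021 the last date on which a questionnaire may fall due, and count returns until the section 7.7 chase is complete or the data are frozen. Correct the misprinted year.
2. Set posting dates for April–June operations early enough within the permitted range for the full chase to finish.
3. Report capture and loss to follow-up separately for patients with and without a complete chase, and state that an incomplete chase is not counted as loss to follow-up.
4. At the same time, reconcile the 4-month earliest collection in section 7.6 with the 3-month July row and with Table B's allowance.

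The cost is protocol wording plus either a possible short delay to data freeze or slightly shorter follow-up for some patients. No new patients or procedures are needed. The protocol does not show how much delay the study timetable could absorb, so the sponsor should check that first.

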## 10.4 Healthcare Resource use

NICE recommend economic evaluations adopt a healthcare system perspective, therefore only those costs that impact the healthcare sector should be considered and is also in line with a recently published cost-effectiveness analysis of alternative

**IRAS Ref: 271885** Page 48 of 89

prosthetic implants for total hip replacements. A bespoke healthcare resource use survey has been designed to ask patients to self-report their use of healthcare services and resources at baseline (for the previous 6 months) and then again at 3-6 months follow-up. The questionnaire asks patients to consider their use of the following NHS services and/or resources: inpatient stay, outpatient appointment, one-day appointment, accident and emergency services, primary care, community-based services including occupational therapists, and medications prescribed.

These data will be combined with those collected by the scrub team on the day of surgery.

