#### 12.7.2 Reporting period

The period for the reporting of Safety Events ranges from the start of the total hip arthroplasty operation (i.e. knife to skin) until the patient's participation in the study is complete.

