## 12.8.3 Timeframe categories

- Intra-operative: AE occurred between the start and end of the total hip arthroplasty operation, i.e. knife to skin, to when the application of the dressing is completed.
- Early post-op: AE occurred any time after the end of the total hip arthroplasty operation, up to and including 6-weeks post-operation (i.e. 42 days, with the day of the operation being day 0).
- Late post-op: AE occurred any time in or after the seventh week post-operation (i.e. from and including day 43, with the day of the operation being day 0).

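### Section 7.6 does not carry over the 6-week AESI enquiry and section 7.7 states no record check for non-responders, so late medical AESIs of grade 3 or above may be under-ascertained

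*Protocol*

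**What the plan says.** - **6 weeks (Protocol 7.5).** "Data will also be collected Adverse Events of Special Interest; these will primarily be surgical complications, such as but not limited to returns to theatre". Antibiotic prescriptions and unplanned contact about the surgery are also noted.
- **3-6 months (Protocol 7.6).** Patients are "asked about any return to theatre required and any unanticipated contact with the surgical team or GP regarding the surgery". No AESI prompt and no antibiotic question appear. A phone call precedes the postal pack, but the section does not say whether these questions are put in that call or in the pack.
- **Non-response (Protocol 7.7).** After two reminder calls and a letter, "the patient shall be classed as lost to follow-up" and a form goes to the trials centre. No look at hospital or GP records is stated.
- **How long safety runs.** Section 12.7.2 keeps reporting open until the patient's "participation in the study is complete". Section 12.8.3 defines a late category: "AE occurred any time in or after the seventh week post-operation". Outcomes 4.ii (revision) and 4.iii (re-operation for infection) in section 11.2.2 are counted within 3-6 months.
- **Other routes to late events.** Section 12.7.1 says that safety events are found through enquiries at study time points and through emergency admissions, and gives patients a contact card. Table B marks safety reporting at 3-6 months. The resource use survey at that time asks about "inpatient stay, outpatient appointment, one-day appointment, accident and emergency services, primary care" and prescribed medication (section 10.4).
- **What is reportable (Protocol 12.3).** AESIs of Clavien-Dindo grade 3 or above, and serious device-related events.

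**The concern.** The enquiry narrows between 6 weeks and the last contact, while the reporting obligation does not. A serious medical event in, say, week 10 that another team treats is not a return to theatre. The patient may also not regard it as contact about the hip operation. Someone who answers both questions in section 7.6 accurately could leave it out.

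For postal non-responders the protocol specifies no late ascertainment beyond chasing the pack. Their revision and re-operation status may be unknown even where the operating hospital's own records would settle it.

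At stake are the late part of secondary objective 5 (intra- and post-operative safety), the completeness of outcomes 4.ii and 4.iii, and the data on which the steering committee relies to oversee complications, since there is no separate safety committee (section 18.3). A feasibility study is also where the follow-up method of the full trial is tried out.

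**Working it through.** The protocol gives no figure for late-event capture to reproduce. The check compares the passages and then sizes the gap.

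**1. How much of the safety period is late.** Taking 3 months as 90 days and 6 months as 183 days, day 43 onward is (90 - 42)/90 = 48/90 = 53% of the period for a July operation, and (183 - 42)/183 = 141/183 = 77% for a January-April operation. This is a share of days, not of events.

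**2. Which event types the two questions miss.** Table C lists 19 AESIs. One (fracture during the operation) is intra-operative only, leaving 19 - 1 = 18 that could occur late. By our classification:

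| Group | Count | Share of 18 |
|---|---|---|
| Local hip, wound or implant events | 12 | 67% |
| Medical events: cerebrovascular accident, deep vein thrombosis, myocardial infarction, organ failure, pneumonia, pulmonary embolism | 6 | 33% |

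Only grade 3 and above is reportable. Under Table D, grade 3 means a surgical, endoscopic or radiological intervention, so the return-to-theatre or surgical-contact question would usually pick up the 12 local types. It would not directly pick up the 6 medical types. At grade 4, which means life-threatening and needing intermediate or intensive care, these are among the most serious events in the list.

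**3. Whether another route closes the gap.**

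| Route | What it adds | What is left open |
|---|---|---|
| 12.7.1 enquiry rule | Active enquiry at study time points | The only safety questions that 7.6 specifies for this time point are the two narrow ones |
| 12.7.1 card | Emergency admissions can be passed to the research team | Depends on the patient or the admitting team using it |
| Table B safety row | Safety reporting marked at 3-6 months | Speaks of serious adverse events or incidents; AESIs, reportable under 12.3, are not named |
| Resource use survey | Inpatient, A&E, primary care, medication | No step passes answers to safety reporting; absent for non-responders |
| 7.9 | Re-interventions recorded in notes and on a CRF | No instruction to look for them before a patient is closed as lost |

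Each route helps, but none requires the medical AESIs to be asked about at 3-6 months.

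**4. Non-responders.** The protocol gives no expected rate. Assume 5% to 30% of 40, that is 40 x 0.05 = 2 to 40 x 0.30 = 12 patients, and assume that none of them was asked the questions by phone. Assume also a late reportable event risk p of 2% to 5% per patient. The chance of at least one such event among m patients is 1 - (1 - p)^m:

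- m = 2, p = 0.02: 1 - 0.98^2 = 4%
- m = 12, p = 0.05: 1 - 0.95^12 = 46%

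One missed event among 40 patients moves an overall rate by 1/40 = 2.5 percentage points.

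**The case against.** The strongest reply is that section 12.7.1 already requires enquiry at every study time point and Table B marks safety reporting at 3-6 months with the same row as at 6 weeks. On that view section 7.6 merely adds two specific questions. Section 12.8 also calls itself an overview and points to a Safety Plan that was not available to us. This stands in part: the late enquiry is not confined to the two questions by rule. But section 7.6 is where the enquiry at that time point is spelled out, and staff who follow it would not be led to the medical AESIs.

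Four stronger inferences are tempting, and the documents do not support them.

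- *Most late AESIs are missed.* Only grade 3 and above counts, and 12 of 18 types would usually surface through the existing questions. Pneumonia or embolism treated with drugs alone is grade 2 and not reportable. Grade 4 events would normally involve an emergency admission, a route that section 12.7.1 names.
- *Non-responders are counted as event-free.* Nothing says so. They are chased three times, and section 11.2.2 reports loss to follow-up and missing data. Because section 7.6 does not place the safety questions in the pack, an unreturned pack does not prove that they went unasked.
- *All complication outcomes have a 3-6 month window.* Only 4.ii and 4.iii do; 4.viii states none. Both 4.ii and 4.iii are returns to theatre, which section 7.6 asks about directly, so the difficulty there is confined to non-responders.
- *The narrow questions cover nearly all of follow-up.* That assumes a 6-week visit at its earliest, 3 weeks. At its latest, 12 weeks (84 days), the share remaining is (90 - 84)/90 = 7% to (183 - 84)/183 = 54%.

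**Conclusion.** The point holds in a limited form. Section 7.6 does not carry over the explicit AESI collection of section 7.5, and section 7.7 states no record check before a patient is closed as lost. Late medical AESIs of grade 3 or above, about a third of the late-possible types in Table C, may therefore be under-ascertained, and revision and re-operation for infection may be unknown in non-responders.

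Severity is minor to moderate. The trial has 40 patients and plans no formal safety comparison (section 11.5), and what section 11.3 carries into the full trial's sample size is PROM variability, retention and clustering, not complication rates. The conclusion rests on our classification of Table C. The 4% to 46% range rests on assumed non-response and event rates, not on figures in the protocol. The Safety Plan may add detail, but it would not remove the mismatch between sections 7.5, 7.6, 12.3 and Table B.

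**What to change.** 1. In section 7.6, use the Table C AESI prompt of the 6-week contact, covering the time since last contact, at the planned pre-notification call or with the pack. State which.
2. In section 7.7, before a patient is classed as lost, have the site check its own hospital record for revision, re-operation for infection and Table C events of grade 3 or above, up to the end of that patient's window.
3. Let an inpatient or A&E entry on a returned Healthcare Resource Use Survey prompt the same check.
4. Align the Table B safety row with the reportable categories in section 12.3, so that AESIs are named.

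The cost is wording in three places and a few minutes of site time per patient for 40 patients, using a call and a survey already planned. Events treated at other hospitals may still be missed in non-responders, and the report should say so.
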